8.6.1 Responder Rates Based on mBPI Pain Intensity

Pain intensity score reduction based on the mBPI Pain Intensity subscale for each visit will be used to classify responder where:

Pain intensity score reduction = (mBPI Pain Intensity change from visit 3/visit 3 mBPI Pain Intensity)*100.

Three responder rates will be calculated at each time point, where responders are defined as subjects with:

- Pain intensity score reduced by 30% from visit 3 mBPI Pain Intensity,
- Pain intensity score reduced by 50% from visit 3 mBPI Pain Intensity,

- Pain intensity score reduced according to multiple cut-offs of 10% increments from the visit 3 mBPI Pain Intensity.

Responder rate = (no. of responders / total no. of subjects)*100, where total no. of subjects is the number of all the subjects in the analysis set. Subjects, who discontinue prior to the time point or have a missing pain score at that time point, will be counted as non-responders.

The number and percentage of responders in each dose level for pain intensity score reduction according to multiple cut-offs of 10% increments from baseline will be presented.

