7.1 General Considerations

Generally, if not specified, continuous data will be summarized by descriptive statistics (n, mean, standard deviation, median, minimum, maximum). Categorical data will be summarized by the number and percentage of subjects. All assessments, if necessary, will be summarized by Denovo naive, Denovo opioid experienced, Rollover by treatment received in feeder study. All statistical tests, as deemed necessary, will be 2-sided with a significance level of 5%.

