7.2 Study Day

- The day of the titration start (Visit 3 date) will be called Titration Day 1. Visit 10 is the end of titration, the dose at visit 10 is defined as stable dose. The day of the stable dose (Visit 10 date) will be called Day I. Study day will be calculated from the Day 1.
- Baseline is defined as the last non-missing observation prior to or on Titration Day 1. Change from baseline variables will be calculated as the post-baseline value minus baseline value.

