7.3 Analysis Sets

Denovo opioid experienced subjects are defined as de novo subjects who are currently taking no less than 10 mg but no more than 60 mg MSE/day for at least the 7 days prior to signing the ICF

Denovo naive patients are defined as de novo subjects who are not opioid experienced subjects.

Safety Analysis Set: The Safety Analysis Set includes all subjects who received at least 1 dose of study drug. Analyses of safety will be summarized for this population.

Completers Analysis Set: All subjects in the Safety Analysis Set who complete 52-week exposure to NKTR-181.

Pharmacokinetic (PK) Analysis Set: The PK Analysis Set consists of all subjects who received at least 1 dose of NKTR-181 and have at least 1 PK data point available.

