8.6 Efficacy Endpoint

The mBPI-SF will be assessed at each visit during the study. The mean of the 4 intensity items (3-6) will be calculated and used as a measure of pain severity. The mean of the 7 interference items (9A-9G) will be calculated and used as a measure of Pain interference. Change from baseline to each month (visit) will be calculated for the Pain severity, Pain interference, and each individual score, if applicable.

If there are missing items when the pain severity score and pain interference score are calculated, the mean of the completed items in one dimension (dimensions include pain severity and pain interference) will be imputed to substitute the missing item, provided that more than 50% of the items in one dimension are completed ([Halling, 1999](#)).

The change from baseline and value for mBPI-SF dimensions and individual scores at each visit will be summarized descriptively over time.

In addition, an exploratory analysis will be performed on mBPI. The change from baseline to the end of the long term safety study will be analyzed. Baseline will be considered as last non-missing assessment on or prior to the first dose in this long term safety study (visit 3). The change from baseline will be analyzed using Mixed Model Repeated Measure (MMRM) analysis. The model will include change from baseline as dependent variable, baseline score as a covariate, subject's status (De Novo or Rollover with NKTR-181 or Rollover with Placebo), time, subject's status and time interaction as fixed effects. Point estimates on the Least Squared means over time will be calculated with corresponding 95% confidence intervals different dose levels. These analysis will be applied to both pain intensity and interference based on mBPI. The pain intensity means and LSmeans over time will be present graphically.

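### Minor: the SAP 8.6.1 reduction formula has the wrong sign for its own responder definitions, and the section does not commit to the SAP 7.1 subject groups, whose Visit 3 reference states differ

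*SAP*

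**What the plan says.** **Formula.** SAP 8.6.1 gives "Pain intensity score reduction = (mBPI Pain Intensity change from visit 3/visit 3 mBPI Pain Intensity)*100" as the quantity that classifies responders. The sign convention is in SAP 7.2: "Change from baseline variables will be calculated as the post-baseline value minus baseline value". The definitions that follow the formula are worded as falls in pain, for example "Pain intensity score reduced by 30% from visit 3 mBPI Pain Intensity", with a matching 50% definition and a series in steps of 10%.

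**Denominator and breakdown.** The rate is the number of responders over the total number of subjects, "where total no. of subjects is the number of all the subjects in the analysis set". The only breakdown that 8.6.1 names is dose: "The number and percentage of responders in each dose level for pain intensity score reduction".

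**Subject groups elsewhere.** SAP 7.1 has a general but conditional rule: "All assessments, if necessary, will be summarized by Denovo naive, Denovo opioid experienced, Rollover by treatment received in feeder study". SAP 7.3 defines the two De Novo groups, the second by exclusion: "Denovo naive patients are defined as de novo subjects who are not opioid experienced subjects". The exploratory MMRM in SAP 8.6 has a three-level status factor ("De Novo or Rollover with NKTR-181 or Rollover with Placebo") and its interaction with time. Protocol 11.1 promises separate De Novo and Rollover summaries for long-term safety, and does not split Rollovers by feeder treatment. Protocol 11.10.1 plans only mBPI-SF values and changes, so it contains no responder definition.

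**State at Visit 3.** Rollovers come from NKTR-181 or placebo (Protocol 6.1), must have had no interruption of study drug (5.1.1), and reach Visit 3 after tapering to this study's starting dose (6.1.1). Opioid-experienced De Novo subjects reach it after an opioid taper to no more than 30 mg MSE/day (6.1.2, 6.6.1). De Novo subjects stop all current analgesics at Visit 3 (6.2), and all subjects then begin dosing in this study.

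**The concern.** There are two separate issues in one section.

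First, a derivation formula in a SAP is what a programmer implements. Combined with SAP 7.2, this one returns a negative reduction for every subject who improves and a positive one for every subject who worsens. Nothing elsewhere in the SAP or protocol sets another sign convention.

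Second, a percentage fall from Visit 3 does not mean the same thing in each group. An NKTR-181 Rollover whose score stays at its Visit 3 level has a 0% reduction and meets neither the 30% nor the 50% definition, however well the pain is controlled. One whose pain rose during the feeder-study taper and later fell may meet them. For an opioid-experienced De Novo subject, the change from Visit 3 follows the loss of previous analgesics as well as the start of NKTR-181. A single rate over all subjects averages these different quantities with weights set by enrolment. The mBPI-SF is the measure named in the secondary objective, so readers are likely to use the responder tables.

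**Working it through.** The documents state no responder rate, so there is no planned figure to reproduce.

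**1. Sign of the formula.** Inputs: the 8.6.1 formula, the 7.2 convention, and the 0 to 10 pain scale on which lower is better (SAP 6.1.1).

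- As written: 100 × (visit − Visit 3)/Visit 3
- Corrected: 100 × (Visit 3 − visit)/Visit 3

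| Visit 3 → visit | As written | Corrected | Worded definition, read as at least |
|---|---|---|---|
| 6 → 4 | −33.3 | +33.3 | meets 30% |
| 6 → 3 | −50 | +50 | meets 30% and 50% |
| 6 → 4.2 | −30 | +30 | meets 30% |
| 6 → 6 | 0 | 0 | meets neither |
| 6 → 8 | +33.3 | −33.3 | meets neither |
| 4 → 6 | +50 | −50 | meets neither |

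Taken literally, no improved subject can reach a positive cut-off, while a subject who worsens by 30% can. The corrected form agrees with the worded definitions in every row.

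**2. Dependence of the pooled rate on mix.** Inputs from the documents: about 600 subjects, of whom about 250 are De Novo (Protocol 4.1, SAP 4.0), leaving 600 − 250 = 350 Rollovers. The total may move in either direction (Protocol 11.2). Not given, and therefore assumed: s, the NKTR-181 share of Rollovers; r, the response rate of NKTR-181 Rollovers; p, the rate in everyone else.

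- w = 350s/600, the NKTR-181 Rollover share of all subjects
- Pooled rate = w·r + (1 − w)·p, so its shift from p is w × (r − p)

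| s (assumed) | w | r − p = −30 points | r − p = 0 | r − p = +30 points |
|---|---|---|---|---|
| 25% | 14.6% | −4.4 | 0 | +4.4 |
| 50% | 29.2% | −8.8 | 0 | +8.8 |
| 75% | 43.8% | −13.1 | 0 | +13.1 |

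A second illustration holds the group rates fixed and changes only enrolment. Assume 30%-responder rates of 45% (De Novo), 35% (Rollover-placebo) and 25% (Rollover-NKTR-181), N = 600, and Rollovers split equally by feeder treatment.

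- 250 De Novo: (0.45 × 250 + 0.35 × 175 + 0.25 × 175)/600 = 217.5/600 = 36.25%
- 350 De Novo: (0.45 × 350 + 0.35 × 125 + 0.25 × 125)/600 = 232.5/600 = 38.75%
- 150 De Novo: (0.45 × 150 + 0.35 × 225 + 0.25 × 225)/600 = 202.5/600 = 33.75%

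With equal rates of 40% in all groups, the pooled rate is 40.0% for any mix.

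**3. Rates by dose.** On the same assumed rates, the average Rollover rate is (35 + 25)/2 = 30%. A dose level with 20% De Novo subjects would show 0.2 × 45 + 0.8 × 30 = 33.0%. One with 80% would show 0.8 × 45 + 0.2 × 30 = 42.0%, with no dose effect at all. A larger problem remains after grouping. Under Protocol 6.2 the dose is chosen on the investigator's judgement of effectiveness and tolerability, so the dose reached is itself partly a result of response.

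**The case against.** **The sign is a notation slip.** The quantity is called a reduction and every definition below it is worded as a fall, so a competent programmer would code it correctly. That stands, and it is why the practical risk is low. A reader might infer that the published rates will be inverted; the documents do not support that. The line still contradicts the definitions it serves.

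**Grouping is already provided for.** SAP 7.1 covers all assessments and names the relevant groups, and the MMRM models the same score with status and status by time. This largely stands. It would be wrong to say that the SAP has no such groups. What remains is that 7.1 is conditional, 8.6.1 does not adopt it, and the MMRM factor does not change the responder tables. The MMRM in fact shows that the SAP treats status as relevant to change from Visit 3.

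**The SAP never says that the rate measures response to starting NKTR-181.** Correct. The request is for clear labelling and does not allege a false claim.

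**De Novo subjects are not an untreated reference either.** This also stands. A reader might infer that only the NKTR-181 Rollovers have an awkward baseline and that the De Novo rate is a clean response to NKTR-181. The De Novo opioid taper and the stopping of all analgesics at Visit 3 rule that out, so every group's reference state needs stating.

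**The magnitudes are invented.** They are illustrations on assumed rates and shares, symmetric about zero, and say nothing about what this trial will show.

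**Conclusion.** Both parts hold, and the point is minor.

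The sign error is certain from SAP 7.2 and 8.6.1 together: improvement is negative and worsening positive. The evident intent makes it a low-risk, one-line correction.

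The grouping gap is one of commitment. If response differs by group, the pooled rate depends partly on enrolment mix; if it does not, there is no effect. Over the assumed ranges the shift runs from −13.1 to +13.1 points, but the documents give neither the feeder-treatment split nor any group rate, so the actual size and direction cannot be computed. It is tempting to infer that NKTR-181 Rollovers must pull the pooled rate down. That does not follow, because pain may have risen during their taper and then fallen. The documents also do not describe what placebo Rollovers were taking up to Visit 3, so nothing is concluded about them.

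By-dose rates are confounded by titration whatever the mix, and grouping by status does not cure that. The responder analysis is a descriptive addition in the SAP; no test, power or primary objective is affected.

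**What to change.** In SAP 8.6.1:

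1. Replace the formula with reduction = 100 × (Visit 3 score − visit score)/Visit 3 score, and write *at least* for each cut-off.
2. Commit to presenting the responder rates by the SAP 7.1 groups (De Novo naive, De Novo opioid experienced, Rollover-placebo, Rollover-NKTR-181), each with its own denominator, beside the pooled rate. The two De Novo groups may also be shown combined, to match the MMRM status factor.
3. State each group's Visit 3 reference state in the text and table footnotes, including the De Novo groups and not only Rollover-NKTR-181.
4. Describe the by-dose rates as confounded by titration to effectiveness and tolerability.

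A rule for a Visit 3 score of 0, where the ratio is undefined, is optional wording.

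The cost is one corrected line, a few sentences, and a few more descriptive tables with smaller groups. No new data are needed. By-dose tables within groups need not be required: 4 groups × 6 dose levels is 24 cells per visit, many of them likely to be sparse.

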1.1 Study Schematic

1.2 Schedule of Assessments

Assessment Period	Screening Up to 21 days		Treatment* 52 weeks							Follow-Up 14 days		Unscheduled Visit
	1	2 ¹	3	4, 5, 6, 7, 8, 9 (Flexible)	10, 13, 17, & 20	11 & 12	14-16 & 18-19	21/ET ²	22/EOT	23	24/EOS	
Dayse	≤ 21 days prior to Visit 3		1	Every 4-10 Days after previous visit	Every 30 (- 3)	Every 30 (- 3)	Every 30 (- 3)	D357 (+ 3)	D364 (+ 3)	72 hours	14 (± 2)	
Written informed consent	X											
Inclusion/exclusion criteria	X	X	X									
Demographics ³	X											
PHQ-8 ⁴	X											
Medical history ⁵	X											
Alcohol breath test ⁶	X											
Physical examination ⁷	X											
Vital signs ⁸	X		X	X	X				X	X		X
12-lead electrocardiogram ⁹	X				X				X			X
Clinical laboratory tests ¹⁰	X		X	X	X	X		X	X	X	X	X
Pregnancy test ¹¹	X		X		X				X			X
Urine drug screen ¹²	X		X	X	X							
eC-SSRS ¹³	X		X		X			X	X			
Taper opioid analgesics ¹⁴		X										
Dose titration assessment				X								
mBPI-SF ¹⁵			X	X	X	X	X		X			X
COWS		X ¹⁶	X ¹⁶					X	X	X	X	X
SOWS ¹⁷		X						X	X	X	X	
PK blood sample collection			X ¹⁸	X ¹⁹	X	X		X	X			X
Discontinue current analgesics			X									
Dispense/review/collect/instruct study drug			X	X	X	X	X	X ²⁰	X ²¹			X
Opioid side effect training			X									
Abuse & diversion assessment				X	X	X	X		X			X
Concomitant medications ²²			←									X
Adverse events ²²			←									X

Abbreviations: ALP, alkaline phosphatase; ALT, alanine aminotransferase; AST, aspartate aminotransferase; BMI, body mass index, COWS, Clinical Opiate Withdrawal Scale; eC-SSRS, electronic Columbia–Suicide Severity Rating Scale; ECG, electrocardiogram, EOS, end of study; EOT, end of treatment; ET, early termination; mBPI-SF, modified Brief Pain Index-Short Form; MSE, morphine sulfate equivalent; NRS numerical rating scale; PHQ-8, Personal Health Questionnaire Depression Scale PK, pharmacokinetic; SOWS, Subjective Opiate Withdrawal Scale; TBL, total bilirubin.

* If at any time a subject does not tolerate study drug between protocol-mandated visits in the Treatment Period, per Investigator discretion, an unscheduled visit should occur.

FOOTNOTES:

1. There is no Visit 2 for Rollover Subjects.
2. If a subject was dosed with study drug and discontinues from the study before completing all of the scheduled assessments, then assessments for Visit 21/ET and all safety follow-up procedures should be completed for this subject.

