2.3 Study and Dose Rationale

This study is designed to provide adequate safety data in subjects with chronic low back pain or chronic noncancer pain in order to fulfill ICH requirements for new chemical entities. The dose range to be utilized is 100-mg NKTR-181 twice daily (BID) to 600-mg NKTR-181 BID. This dose range has been established based upon safety, tolerability, pharmacokinetic (PK), and pharmacodynamic (PD) data from three Phase 1 studies and the findings of a completed Phase 2 study in opioid-naïve subjects with moderate to severe chronic pain due to osteoarthritis of the knee. Phase 1 multiple ascending dose (MAD) studies established a dose that was not tolerated in opioid-naïve, healthy subjects (500-mg NKTR-181 every 12 hours [q12h]) and demonstrated 400-mg NKTR-181 q12h to be a safe and well-tolerated dose. In both studies, pupillometry

demonstrated robust CNS mu-opioid agonist effects consistent with known, approved extended-release/long-acting (ER/LA) opioids.

Evidence supporting the minimum dose of 100-mg NKTR-181 BID comes from the Phase 1 clinical program and a completed Phase 2, enriched-enrollment, randomized withdrawal design study in approximately 200 subjects with moderate to severe chronic pain due to osteoarthritis of the knee. In this Phase 2 study, 49% of subjects were randomized at 100-mg NKTR-181 BID and an average 40% reduction in average daily pain scores was demonstrated during the open-label titration period, consistent with known, approved opioid analgesics.

Recently, over 330 opioid-naïve subjects gradually titrated to a dose of 400mg q12h in the ongoing Phase 3 study (14-181-07) have shown a good safety and tolerability profile. In addition, the current long term safety study (14-181-08) and the second efficacy study (14-181-12) both allow inclusion of opioid-experienced subjects who are expected to tolerate higher doses of NKTR-181. Thus, titration to a maximum dose of 600mg q12h will be allowed in a measured step-wise approach starting at the lowest dose available so as to ensure tolerability while managing chronic pain.

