Subjects will return to the clinic for assessments of tolerability and effectiveness every 4 to 10 days for up to 6 more times over a 5-week period until a stable dose is achieved. A **stable** dose is a dose that is effective and tolerated on two sequential visits (i.e., after at least 8 days of continuous treatment). Subjects who continue to tolerate study drug but do not have adequate relief of pain, based on the Investigator's clinical judgment, will continue dose escalations of 100-mg BID increments until the maximum dose of 600-mg NKTR-181 BID is reached.

Subjects who do not achieve adequate pain control at 600-mg NKTR-181 BID will be classified as non-responders and will be discontinued from further participation in the study.

Non-responders will be required to complete the ET Visit (Visit 21/ET) and safety follow-up requirements.

Subjects will begin a monthly clinic visit schedule after a tolerable, effective and stable dose is achieved. **Doses of NKTR-181 may be adjusted upwards (up to a maximum dose of 600-mg NKTR-181 BID) or downwards as needed during the Treatment Period, based on the Investigator's (or qualified sub-Investigator's) assessment of effectiveness and tolerability.**

If at any time a subject cannot tolerate study drug between protocol-mandated visits, per Investigator discretion, an unscheduled visit should occur. For subjects with tolerability issues, the dose of NKTR-181 may be adjusted downwards, as necessary, based on the Investigator's clinical judgment in a stepwise 100-mg changes (e.g., 300-mg BID may be lowered to 200-mg BID). Dose adjustments may occur at unscheduled visits, however, an unscheduled visit will not replace a regularly scheduled visit, and the subject should be seen at all regularly scheduled visits.

Throughout the Treatment Period, subjects who experience breakthrough pain will be allowed rescue medication, as outlined in Section 6.4. Note: If subject is off of study drug for 3 days or more, sponsor **must** be consulted prior to restarting study drug.

Subjects will report their pain experience at each visit using the mBPI-SF. At quarterly intervals, subjects will be assessed for vital signs, 12-lead electrocardiogram (ECG), and clinical laboratory testing.

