7.4 Definition of Visit Window

Deviations are to be expected between subjects in the actual number of study days from Day 1 to when planned visits are carried out. To handle this for tables, figures, listings, and analyses where data are to be grouped by visit, visit numbers will be defined according to [Table 1](#).

The following windows will apply only for summaries for value and change value by visit and summaries for abnormalities. If multiple assessments were performed within the visit window, the following will be applied:

- If there are multiple records in the same visit window, the measurement closest to the scheduled visit day will be used.
- If two visits are equidistant from the scheduled day, the later will be assigned to the visit.
- In the summaries for abnormalities, the worst case will be summarized for that visit regardless of how close to the scheduled visit it is.

Table 1: Windowed Visits for Summary

Visit	Scheduled Study Day	Windowed Visits for Labs	Windowed Visits for Vital Signs	Windowed Visits for ECG	Windowed Visits for CSSRS	Windowed Visits for mBPI	Windowed Visits for COWS
Baseline	First dose	<=first dose date	<=first dose date	<=first dose date	<=first dose date	<=first dose date	<=first dose date
The Titration visits		go with the actual visit	go with the actual visit	NA	NA	go with the actual visit	NA
Visit 10 - Stable Dose	1	Day 1	Day 1	Day 1	Day 1	Day 1	NA
Visit 11	30	Day2 to 45	NA	NA	NA	Day2 to 45	NA
Visit 12	60	Day46 to 75	NA	NA	NA	Day46to 75	NA
Visit 13	90	Day76 to 105	Day2 to 105	Day2 to 105	Day2 to 105	Day76 to 105	NA
Visit 14	120	NA	NA	NA	NA	Day106 to 135	NA
Visit 15	150	NA	NA	NA	NA	Day136 to 165	NA
Visit 16	180	NA	NA	NA	NA	Day165 to 195	NA
Visit 17	210	Day106 to 225	Day106 to 225	Day106 to 225	Day106 to 225	Day196 to 225	NA
Visit 18	240	NA	NA	NA	NA	Day226 to 255	NA
Visit 19	270	NA	NA	NA	NA	Day256 to 285	NA
Visit 20	300	Day226 to one day before visit 21	Day226 to one day before visit 21	Day226 to one day before visit 21	Day226 to one day before visit 21	Day286 to one day before visit 21	NA
Visit 21	357 from Titration Day 1	go with the actual visit	NA	NA	go with the actual visit	go with the actual visit	go with the actual visit
Visit 22	364 from Titration Day 1	go with the actual visit	go with the actual visit	go with the actual visit	go with the actual visit	go with the actual visit	go with the actual visit

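### The SAP responder rule counts subjects who stabilise early as non-responders at flexible Visits 6-9, which they are not due to attend

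*SAP*

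**What the plan says.** **The rule.** SAP 8.6.1 classifies responders at each visit from the percentage change in mBPI pain intensity since Visit 3: "Three responder rates will be calculated at each time point". The denominator is fixed, "where total no. of subjects is the number of all the subjects in the analysis set". On missing scores it says: "Subjects, who discontinue prior to the time point or have a missing pain score at that time point, will be counted as non-responders". It makes no exception for a visit that was not due and does not list the time points. It also asks for the 10%-increment results by dose level.

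**The visits.** The Schedule of Assessments (Protocol 1.2) labels Visits 4 to 9 as flexible, each 4 to 10 days after the previous one, and marks the mBPI-SF there. Under Protocol 6.2, after the first return visit subjects come back "every 4 to 10 days for up to 6 more times over a 5-week period until a stable dose is achieved". A stable dose is one judged effective and tolerated at two sequential visits. Then: "Subjects will begin a monthly clinic visit schedule after a tolerable, effective and stable dose is achieved". SAP 7.2 makes Visit 10 the end of titration and the stable-dose visit for everyone.

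**The concern.** Counting a missing score as failure is usually defended as conservative, because people who stop attending are more likely to be doing badly. At Visits 6-9 the reasoning runs the other way. A subject has no score there because the investigator has already judged the dose effective and tolerated, and the visit was not needed. The rule turns that success into a non-response.

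At stake is the reading of the mBPI responder table during titration. The mBPI-SF is the study's only secondary objective. If the SAP is programmed as written, the responder rate would dip over Visits 6-9 for a reason unrelated to pain. The dip would also differ by dose level: all subjects start at 100 mg BID and move in 100-mg steps, so those who settle on a lower dose can leave the flexible visits sooner.

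**Working it through.** The plan states no responder rate and has no formal sample size calculation (Protocol 11.2), so there is no figure to reproduce. The check asks how high the reported rate can go.

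**Inputs from the documents**
- Fixed all-subjects denominator, missing counted as non-response (SAP 8.6.1).
- Start at 100 mg BID at Visit 3, 100-mg steps, stable after two sequential effective and tolerated visits, then monthly visits (Protocol 6.2).
- About 600 subjects (Protocol 11.2).
- "49% of subjects were randomized at 100-mg NKTR-181 BID" in the Phase 2 study (Protocol 2.3). This is used only as one illustrative value and is not a planning figure for this trial.

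**Assumptions:** the share already stable, the spread over doses and the response rates. None is given in the documents, so ranges are shown. Discontinuation is ignored.

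**Step 1. Earliest stable visit.** With one step per visit, dose level k (k = 0 for 100 mg, up to 5 for 600 mg) starts at Visit 3 + k and can be confirmed at Visit 5 + k.

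| Dose (BID) | Earliest stable visit | Flexible visits then not held |
|---|---|---|
| 100 mg | 5 | 6, 7, 8, 9 |
| 200 mg | 6 | 7, 8, 9 |
| 300 mg | 7 | 8, 9 |
| 400 mg | 8 | 9 |
| 500 mg | 9 | none |
| 600 mg | 10 | none |

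Visits 4 and 5 are not affected.

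**Step 2. Ceiling at Visit 6.** Let s be the share stable at Visit 5. Those subjects have no Visit 6 score, so the rate is at most 1 - s even if every subject responds.

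| s | Subjects of 600 | Ceiling |
|---|---|---|
| 10% | 60 | 90% |
| 25% | 150 | 75% |
| 49% | 294 | 51% |
| 60% | 360 | 40% |

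**Step 3. Visits 7-9.** The ceiling at Visit v is 1 minus the share whose stable visit is before v. Three assumed spreads of final dose:

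| Spread, 100 to 600 mg | V6 | V7 | V8 | V9 |
|---|---|---|---|---|
| Six equal shares (1/6 each) | 83% | 67% | 50% | 33% |
| 49%, then 10.2% each | 51% | 41% | 31% | 20% |
| 49 / 20 / 15 / 10 / 4 / 2% | 51% | 31% | 16% | 6% |

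**Step 4. Reported rate against the rate with Visit 5 status kept.** Let r1 be the response rate in subjects stable at Visit 5 and r2 the rate in the rest.
- SAP rule at Visit 6: (1 - s) × r2.
- Visit 5 status kept: s × r1 + (1 - s) × r2.

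With r1 = 80% and r2 = 40% (assumed) and s = 49%, the SAP rule gives 0.51 × 0.40 = 20.4%. Keeping Visit 5 status gives 0.49 × 0.80 + 0.51 × 0.40 = 59.6%. The other shares:

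| s | SAP rule | Visit 5 status kept |
|---|---|---|
| 10% | 36% | 44% |
| 25% | 30% | 50% |
| 60% | 16% | 64% |

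**Step 5. Two apparent ways out.**
- Reading missing as missing when due changes nothing: the subject stays in the fixed denominator and cannot be in the numerator.
- Dividing by attending subjects only gives 40% for every s in Step 4. That is also too low, because stable responders have left the denominator.

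**The case against.** **No sentence says that Visits 6-9 are skipped.** This is correct. It is inferred from the flexible label, the upper limit on return visits, the until-stable condition and the move to monthly visits. Protocol 11.10.1 and SAP 8.6 also speak of the mBPI-SF at each visit. That wording does not create a visit that is not held, so the inference remains the natural reading.

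**SAP Table 1 does not settle the matter.** It lists the titration visits for the mBPI, but SAP 7.4 limits its windows to value, change and abnormality summaries. SAP 8.6 also mentions change to each month. So Table 1 cannot prove that Visits 6-9 belong in the responder analysis. The case rests on SAP 8.6.1 itself, which refers to each visit and each time point without limit.

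**The sizes are illustrative.** This stands. The 49% comes from opioid-naïve knee osteoarthritis subjects in an enriched-enrollment design. Protocol 2.3 expects opioid-experienced subjects in this trial to tolerate higher doses.

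**Stronger readings that the documents do not support.**
- A reader might infer that everyone settled on 100 mg would show 0% response at Visits 6-9. That holds only for subjects confirmed at Visit 5. Subjects held at 100 mg for longer, or titrated up and then reduced, attend more visits. SAP 8.6.1 also does not say whether dose level means current, stable or highest dose.
- A reader might infer that by-visit mBPI means at Visits 6-9 describe only uncontrolled subjects. Under Step 1, those attending Visit 6 include 200 mg subjects at their second effective visit. At Visit 9 only 500 mg and 600 mg subjects remain, at their second and first effective visits.

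**Conclusion.** The rule is wrong as written for Visits 6-9 and should be fixed. The reported rate at Visit 6 is capped at 1 minus the share already stable, between 90% and 40% for assumed shares of 10% to 60%, and the cap falls through Visit 9. Lower dose levels tend to be hit hardest, so a by-dose table at those visits could show a pattern that reflects attendance and not response.

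The conclusion rests on two readings: that flexible visits stop at stability, and that each time point includes them. The direction and the ceiling formula need nothing more; the percentages depend on the assumed shares.

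A reader might go further and conclude that the secondary objective is compromised. The documents do not support that. The responder rates are descriptive and appear only in the SAP. No sample size, test or stopping rule depends on them. The planned graphs show pain intensity means and least-squares means, not responder rates. This mechanism does not reach Visit 10 onward, which is most of the 52 weeks, or the primary safety objective.

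**What to change.** In SAP 8.6.1, replace the reference to each time point with a named list:

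1. One end-of-titration time point: the subject's last mBPI after Visit 3 and on or before Visit 10, with subjects who discontinued during titration counted as non-responders.
2. The scheduled mBPI visits from Visit 10 onward, that is Visits 10-20 and Visit 22. Visit 21 is left out because Protocol 1.2 schedules no mBPI-SF there, although SAP Table 1 lists it.

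Keep the all-subjects denominator and the non-responder rule at these time points. State that all-subjects responder rates are not reported at the individual flexible Visits 6-9. Restricting the time points is enough: no change to the meaning of missing and no carry-forward through skipped visits is needed.

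The cost is a few lines of SAP text and a small change to table shells and programs, with no new data. There are two drawbacks. There is no visit-by-visit responder rate during titration. The end-of-titration rate will also be close to the Visit 10 rate, since the two differ only for subjects still on treatment who lack a Visit 10 score.
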